10.1.4 Sensitivity analyses Rank ANCOVA

Similar to the primary analysis a Rank ANCOVA will be modelled in order to provide evidence of the treatment effect in case of violation of normality assumption.

BLOM Ranks will be calculated with the whole sample, regardless of the treatment group. Ties will be ranked with the mean for tied values.

10.1.5 Sensitivity three-parameter sigmoidal Hill dose-response curve analyses

A three-parameter sigmoidal Hill dose-response curve will be fitted to the data using SAS PROC NLIN. The form of the fitted model will be:

$$y = \frac{akD^{e^n}}{(1 - k)b^{e^n} + kD^{e^n}} + \epsilon$$

where:

- y is the outcome
- D is dose
- n is the log shape parameter
- ε is the random error
- a is the maximum effect
- k is a fixed constant where $0 < k \leq 1$
- b is the dose that provides an effect equal to k x a
- for k=0.5 then b=ED50
- for k=0.9 then b=ED90

The parameters a, b and n will be estimated along with their associated SEs and 95% CIs. The dose-response will be displayed in terms of the estimated value for outcome, together with 90% confidence and prediction limits.

A variation on the dose response model will also be evaluated that corrects for placebo:

$$y = P + \frac{akD^{e^n}}{(1 - k)b^{e^n} + kD^{e^n}} + \epsilon$$

where:

- P is the outcome in placebo treated subjects.

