5 SAMPLE SIZE AND POWER ESTIMATION

A total of 200 completed subjects will be evaluated for the study (50 completed subjects per treatment group, with expected early withdrawal rate of around 15%).

The assumptions used for the sample size calculation are a mean absolute change in the Epworth Sleepiness Scale (ESS) from baseline to the end of the 6-week treatment period of at least 3.0 points (minimum change considered as clinically relevant) and a standard deviation of 5.0 (based on a comparable study of Modafinil in a similar population recruited at one centre (3) which showed a standard deviation in the ESS between 3.5 at baseline and 4.8 at the end of the treatment period) and a reduction in ESS of 2.7 points for subjects treated with Modafinil.

The confirmation of the hypothesis of detecting a mean difference in ESS of 3.0 points vs. baseline requires a sample size of 25 subjects per group (intragroup $\Delta=3.0$; $SD=5.0$; two-side $\alpha=0.05$; $\beta=0.20$; power=80%; one-sample t-test).

The additional endpoint of showing a statistically significant difference of at least 3.0 points in ESS between Bavisant and placebo requires a sample size of 50 subjects per group (between treatment $\Delta=3.0$; $SD=5.0$; two-side $\alpha=0.05$; $\beta=0.20$; power=80%; two-sample equal-variance t-test).

The effect size of Bavisant in EDS is unknown and smaller changes in ESS may be clinically useful according to its profile, and higher variability is expected in this multicentre study; so the sample size of 200 completed subjects (50 per treatment group) is proposed in order to cover both the confirmation of an intragroup change of at least 3.0 points vs. baseline, and the between-group difference of at least 3.0 points change vs. placebo.

The Maintenance of Wakefulness Test (MWT) will be performed in a minimum of 20 subjects per group (80 overall) in order to be enough to show statistically significant differences if the expected MWT absolute change from baseline differs at least in one standard deviation (effect size = 1.0).

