10 STATISTICAL METHODOLOGY FOR EFFICACY ENDPOINTS

10.1 Primary Efficacy Analysis

ESS mean absolute change from baseline to the end of the 6-week treatment period will be analysed with an ANCOVA model, with the baseline ESS as a covariate, region and treatment as a factor. Least-squared (LS) absolute mean changes will be presented by treatment group along with their associated 95% CIs and 2sided p-values; these data will then provide estimated for the within arm change from baseline. The difference between each of the 3 dose arms and the placebo arms in Least-squared (LS) absolute mean changes will also be presented together with the corresponding 95% confidence interval and 2-sided p-value. These paired comparisons will be performed without any multiplicity adjustment. Also, the 4 degrees of freedom (DF) associated with the overall F-test for differences between the treatment arms will be decomposed using Type I sums of squares into three orthogonal single DF contrasts to estimate the linear, quadratic and cubic components of any potential dose response. Baseline data will be imputed with the baseline ESS average. Multiple Imputation Jumping to Reference method will be used to impute post-baseline data (see section 10.4.2 for further reference).

10.1.1 Sensitivity analyses missing reductions imputed to 0:

Same primary analysis will be repeated imputing post-baseline missing ESS evaluations to baseline data that is reduction equal to 0.

10.1.2 Sensitivity analyses MMRM Model:

A mixed-effect model with repeated measures (MMRM) approach will be used, under the missing at random framework carried out using an adequate contrast at Week 2 or Week 6, accordingly. The model will include fixed categorical effects of treatment group, region, visit and treatment-by-visit interaction as well as the continuous fixed covariates of mean baseline ESS. This MMRM model will be run with an unstructured correlation matrix to model the within subject errors. In this case missing values will not be imputed, since (MMRM) is handling missing data through the Maximum Likelihood estimation method.

Unstructured covariance matrix is assumed to explain within subject covariance in MMRM method in protecting the type I error rates. In the event if the assumption of unstructured covariance (UN) matrix results in non-convergence of the model, only then the following covariance structures will be considered in the order mentioned below.

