2. The goal is to obtain the values c_1, c_2, c_3 and c_4 that maximize $(c'\mu)^2/(\sum c_i^2/n_i)$ where n_1, n_2, n_3 and n_4 are the sample sizes for placebo, 0.5, 1, and 3 mg/d respectively. To do so, the NLMIXED procedure will be applied on the above-mentioned one-record dataset to obtain the “maximum likelihood” parameters c_1, c_2, c_3 and c_4 using the following likelihood function:

$$ll = (\mu_1 * c_1 + \mu_2 * c_2 + \mu_3 * c_3 + \mu_4 * c_4) ** 2 / (c_1 ** 2 / n_1 + c_2 ** 2 / n_2 + c_3 ** 2 / n_3 + c_4 ** 2 / n_4);$$

There are infinite solutions to the above problem, so we will hold one coefficient to an arbitrary value (e.g. $c_1 = -10$).

3. Finally, the obtained coefficients will be normalized as follows (shown for c_1):

Sponsor BenevolentAI Bio
 Project Code ... BB-2001-201b

$$ncl=c1/(sqrt(c1**2 + c2**2 +c3**2 + c4**2));$$

For validation purposes, the obtained coefficients will be compared with the ones obtained using the dose-finding R package developed by te authors of MCP-Mod.

III. Dose Response Test

For each of the candidate models, dose-response association will be evaluated using the optimal coefficients identified in the previous step. These contrasts will be tested using the PROC GLIMMIX procedure at an one-sided alpha level of 0.025 and multiplicity adjusted p-values will be obtained through parametric resampling ESS mean absolute change from baseline to the end of the 6-week treatment period will be included in the model as dependent variable, dose as fixed factor and baseline ESS as covariate. SAS code like the code below will be used:

```
PROC GLIMMIX;
CLASS DOSES;
MODEL ESS = DOSES BASELINE /NOINT;
LSMEANS DOSES;
ESTIMATE "EMAX1"          DOSES &C11. &C12. &C13. &C14.,
        "EXPONENTIAL"    DOSES &C21. &C22. &C23. &C24.,
        "SIGMOID EMAX"    DOSES &C31. &C32. &C33. &C34.
        / UPPERTAILED ADJUST=SIMULATE (NSAMP=100000 SEED=1234) ;
RUN;
```

IV. Model Selection

The maximum contrast test method will be used to select the best model to be used in the Mod stage. The selected model will be fitted with PROC NLMIXED procedure using SAS code similar to the script below (shown for the Emax model only):

```
PROC NLMIXED;
BOUNDS S2>0, ED50 >0;
PARMS S2 BETA E0 EMAX ED50;
IF DOSE >0 THEN MEAN = E0+(EMAX*DOSE)/(ED50+DOSE) + BETA*BASELINE;
ELSE IF DOSE = 0 THEN MEAN= E0 + BETA*BASELINE;
MODEL ESS ~ NORMAL(MEAN, S2);
RUN;
```

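### The Hill dose-response models in SAP 10.1.5 leave out baseline ESS, which costs some precision and makes the curve not like-for-like with the MCP-Mod curve

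*SAP*

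**What the plan says.** SAP 10.1.5 says: "A three-parameter sigmoidal Hill dose-response curve will be fitted to the data using SAS PROC NLIN". It writes two models. The first has Hill terms in dose and an error; the second adds P for the outcome on placebo. On the response variable it says only that "y is the outcome". For output, "The parameters a, b and n will be estimated along with their associated SEs and 95% CIs", and the curve is displayed "together with 90% confidence and prediction limits". Neither equation has a baseline or region term.

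The other ESS models in SAP 10.1 do adjust for baseline:

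- The primary ANCOVA (10.1) is fitted "with the baseline ESS as a covariate, region and treatment as a factor".
- The MMRM (10.1.2) has baseline ESS as a continuous covariate.
- The MCP-Mod test step (10.1.3, step III) has "dose as fixed factor and baseline ESS as covariate".
- The MCP-Mod curve (10.1.3, step IV) has a baseline coefficient in its NLMIXED code: "PARMS S2 BETA E0 EMAX ED50".

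For planning, SAP 5 takes an SD of 5.0 and cites a single-centre modafinil study with a "standard deviation in the ESS between 3.5 at baseline and 4.8 at the end of the treatment period". Protocol 7.2 gives an SD range of 4.0 to 5.3 and takes the 5.0 from the pitolisant assessment report.

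**The concern.** This is a dose-finding trial, and the Hill fit and MCP-Mod are its two planned fitted dose-response curves. A sensitivity analysis is easiest to read when it changes one assumption, here the form of the curve. As written, the Hill fit also drops a covariate that the SAP uses elsewhere. If the two curves differ, a reader cannot tell whether curve form or missing adjustment is the cause. Variation in baseline ESS that the other models remove also stays in the error term and widens the confidence limits. Baseline ESS is scheduled for every subject on Day -1, and SAP 9.1 imputes it when missing, so availability does not explain the omission.

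**Working it through.** **The plan's own figure.** The documents state no width for the Hill limits. The one calculation that uses these SDs is the 50 per group in SAP 5. By the normal formula, n = 2 × (1.960 + 0.842)² × 5.0² / 3.0² = 43.6, so 44; the t-test gives 45. The t-test needs 50 at an SD of 5.3. This does not affect what follows, which uses only the SDs.

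**Inputs.** Baseline SD 3.5, end-of-treatment SD 4.8 and SD 5.0, read as the SD of change (SAP 5). SD range 4.0 to 5.3 (Protocol 7.2).

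**Implied correlation.** Var(change) = 3.5² + 4.8² − 2 × rho × 3.5 × 4.8, so rho = (12.25 + 23.04 − 25.00) / 33.6 = 0.306.

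**Residual SD with baseline in the model.** 4.8 × √(1 − 0.306²) = 4.57. It is the same whether y is the change or the week-6 score.

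**Width ratio.** If y is change, 5.0 / 4.57 = 1.094: limits 9.4% wider without baseline. If y is the week-6 score, 4.8 / 4.57 = 1.050: 5.0% wider.

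**Range.**

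| SD of change | Correlation | Residual SD | Wider, y = change | Wider, y = week-6 score |
|---|---|---|---|---|
| 4.0 | 0.574 | 3.93 | 1.8% | 22.1% |
| 4.8 | 0.365 | 4.47 | 7.4% | 7.4% |
| 5.0 | 0.306 | 4.57 | 9.4% | 5.0% |
| 5.3 | 0.214 | 4.69 | 13.0% | 2.4% |

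**Simulation, model with P.** With 50 per arm, the SDs above and y as change, fits of the four arm means gave residual SD and confidence-limit ratios of about 1.09. This held for assumed baseline means of 15 and 17 and assumed placebo changes of 0 to −3. In nonlinear Hill fits with P, 95 of 300 simulated trials gave a usable fit both with and without baseline. Among these the median confidence-limit ratio was 1.08 to 1.10 at 0, 0.5, 1, 2 and 3 mg, and 1.15 at 0.75 mg.

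**Model without P.** At D = 0 the Hill term is 0, so the fitted mean is exactly 0 and its confidence limits have zero width with or without baseline. No single percentage can describe this curve. In simulation (arm-mean fits with placebo fixed at 0) the residual SD ratio was 1.08 to 1.09 with a centred baseline term. With a raw, uncentred term it ran from 1.01 to 1.11, depending on the assumed placebo change and baseline mean, because the raw term partly acts as the missing intercept.

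**Prediction limits.** If y is change, the slope on baseline is 0.306 × 4.8 / 3.5 − 1 = −0.58. For a subject of unspecified baseline the variance is 4.57² + (0.58 × 3.5)² = 20.88 + 4.12 = 25.0, so an SD of 5.0 is right. Nominal 90% limits built on 4.57 would cover 2Φ(1.645 × 4.57 / 5.0) − 1 = 87% of such subjects.

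**The case against.** The strongest reply is that the figure is soft and the analysis minor. The 9% treats 3.5, 4.8 and 5.0 as one coherent set, but Protocol 7.2 traces the 5.0 to a different source and indication, and 10.1.5 does not define y. Protocol 7.2 also expects that variability may be lower because entry requires ESS above 12. With an assumed baseline SD of 2.5 and the same slope and residual SD, the SD of change is √(20.88 + (0.58 × 2.5)²) = 4.79, and 4.79 / 4.57 gives about 5%. A baseline-adjusted curve is already planned in MCP-Mod, with a sigmoid Emax among its candidates, and the primary ANCOVA has adjusted linear, quadratic and cubic dose contrasts. Four mean parameters on four dose levels, with few usable fits in simulation, may be the larger precision problem. All of this stands. It makes the gain modest and uncertain, but it gives no reason to leave the covariate out.

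Three stronger readings are tempting and not supported:

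- *The curve is biased.* Doses are randomised. A chance baseline imbalance of 1 point would shift the change by about 0.58 points under these SDs, which is random error.
- *The planned prediction limits are needlessly wide.* For a subject of unspecified baseline they carry the right variance. Narrower limits hold only at a given baseline.
- *Power is lost.* SAP 10.1.5 specifies estimates and plotted limits, with no test, and the primary ANCOVA already adjusts for baseline.

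**Conclusion.** The omission is real, unexplained and not supplied elsewhere in the documents. It costs precision in a sensitivity analysis and adds an avoidable difference between the two fitted curves. In the model with P, confidence limits are about 9% wider than with adjustment if y is the change in ESS and 5.0 is its SD. The figure is about 2% to 13% over the protocol's SD range, and about 5% if y is the week-6 score and 5.0 is still the SD of change. In the model without P the gain varies by dose and is nil at dose 0. The implied correlation of 0.31 is an inference from planning SDs, not a figure in the plan. Region is missing from the Hill fit too, but the MCP-Mod code also omits it, and the documents give nothing to size its effect. This is a low-priority improvement.

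**What to change.** In both equations of SAP 10.1.5 add beta × (baseline ESS − overall mean baseline ESS), and state whether y is the change or the week-6 score. Use the centred form, unlike the uncentred NLMIXED code in 10.1.3, because the first Hill equation has no intercept for a raw baseline term to leave undisturbed. Draw the curve and its confidence limits at the mean baseline ESS. Label any prediction limits as applying to a subject at the mean baseline, or add the baseline contribution (beta² × variance of baseline ESS) so that they apply to a subject of unspecified baseline.

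The cost is one term and one parameter in each PROC NLIN model, plus a figure label. No new data or visits are needed. The change should be made before unblinding.

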4 DESIGN OF THE STUDY

This phase 2b study is designed as multicentre, multinational, randomized, double blind, parallel group and placebo controlled with three doses of Bavisant (0.5, 1, and 3 mg/d) in subjects with excessive daytime sleepiness with Parkinson's disease. This study will involve approximately 230

subjects from around 48 sites globally. Eligible subjects will be randomly allocated at a ratio of 1:1:1:1 to either Bavisant (at doses of 0.5, 1 and 3 mg/d) or placebo. After signing the study informed consent, subjects meeting the UK PDS Brain Bank Clinical Diagnostic Criteria for Parkinson's disease (see details in the protocol Appendix 18.2) will enter a screening period (lasting up to 3 weeks) followed by a baseline period (lasting up to 1 week). Key inclusion / exclusion criteria will be verified to determine subject eligibility at the screening, baseline periods and prior to randomisation, including the suicide risk assessment following the FDA Guidance for Industry on Suicidal Ideation and Behavior. There is a 6 weeks treatment period, starting on Day 1, followed by a safety follow-up at least 4 weeks after completion of the treatment period. Additional unscheduled visits may be required based on the investigators' judgement at the end of study visit or at the safety follow-up. For early termination, all the assessments of the treatment week 6 visit should be performed, if possible, including the safety follow-up 4 weeks after the last investigational medicinal product (IMP) administration. The figure below describes the study flow graphically.

Figure 1

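### The Hill curve in SAP 10.1.5 has as many free parameters as dose means to fit, and no rule covers the frequent case in which no finite estimates exist

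*SAP*

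**What the plan says.** SAP 10.1.5 specifies a three-parameter sigmoidal Hill curve, fitted by PROC NLIN. The free parameters are a (maximum effect), b (the dose giving k times a, so ED50 or ED90 according to k) and n (log of the shape exponent). The constant k is fixed in advance. Of this curve the SAP says: "The parameters a, b and n will be estimated along with their associated SEs and 95% CIs". At dose 0 the formula gives 0, so it has nothing to fit at placebo.

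The section then states: "A variation on the dose response model will also be evaluated that corrects for placebo". This version adds P, described as the outcome in placebo-treated subjects. The SAP does not say whether P is estimated jointly or set to the observed placebo mean. It does not repeat the promise of SEs and CIs for this version, but it offers no other form of inference either.

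SAP section 4 gives four dose levels (placebo, 0.5, 1 and 3 mg/d), allocated 1:1:1:1. Section 10.1.5 sets no parameter bounds, starting values, convergence criterion or fallback. By contrast, the MMRM in 10.1.2 has a rule for non-convergence.

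**The concern.** A Hill curve with a free slope is a demanding model for three active doses. When the number of parameters equals the number of means, nothing is left to judge fit. When the means also fall in a pattern that no Hill curve can follow, the least-squares criterion has no minimum at finite values. PROC NLIN may still print numbers, but they depend on the starting values and the stopping rule.

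The result at risk is a reported ED50 or ED90 with a 95% interval, in a trial described as dose-finding. Without a rule, an arbitrary figure could enter the study report, or a simpler model could be chosen after unblinding.

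**Working it through.** **Inputs.** Doses 0, 0.5, 1 and 3 mg/d (SAP section 4). For the comparison with placebo, SAP section 5 "requires a sample size of 50 subjects per group", with a 3.0-point difference and "a standard deviation of 5.0". Protocol 7.2 gives an SD range of 4.0 to 5.3. The candidate shapes in SAP 10.1.3 are Emax (ED50 0.2), exponential (delta 1) and sigmoid Emax (ED50 1, H 8).

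**The plan's own figure.** The documents give no estimability rate. Their one related figure is 50 per group. A two-sample t-test at SD 5.0 needs 45 for 80% power, and 50 per group gives 84.4%. The figure of 50 matches 80% at SD 5.3. This is a conservative, separate matter; 50 is used below.

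**When finite estimates exist.** Take k = 0.5 (another k below 1 only rescales b) and write h = e^n. For the placebo-corrected curve let f1, f2, f3 be the fitted effects over P at 0.5, 1 and 3 mg/d:

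1/f = 1/a + (b^h/a) × D^(−h), with D^(−h) equal to 2^h, 1 and 3^(−h).

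Hence (1/f1 − 1/f2)/(1/f2 − 1/f3) = (2^h − 1)/(1 − 3^(−h)). The right side rises with h from ln 2/ln 3 = 0.631.

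For a ≠ 0 the 4×4 Jacobian in (P, a, b, n) is non-singular, so any interior stationary point has zero residual. A finite solution therefore needs all of the following:
- observed effects over placebo of one sign, increasing in size with dose;
- a ratio above 0.631;
- a finite implied maximum (1/a > 0 in the direction of effect).

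Plugging in the observed placebo mean for P gives the same condition.

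**Arithmetic check.** True Emax with ED50 1 and a 3-point effect at 3 mg/d gives effects of 1.333, 2 and 3. The reciprocals are 0.75, 0.5 and 0.333, and the ratio is 0.25/0.167 = 1.5. This equals (2 − 1)/(1 − 1/3), so h = 1 is recovered.

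**A simulated failure.** Arm means −0.35, −1.11, −1.32 and −2.75 look like an orderly dose response. The effects over placebo are 0.76, 0.97 and 2.40 in size, with reciprocals 1.316, 1.031 and 0.417. The ratio is 0.285/0.614 = 0.46, below 0.631. Multi-start least squares drove a to about −73,000.

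**Simulation of the placebo-corrected curve.** Arm means had SE 5/√50 = 0.707, with 200,000 trials per shape and a top-dose effect of 3. The analytic condition agreed with multi-start numerical fitting in 60 of 60 trials checked.

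| True shape | Finite estimates exist |
|---|---|
| SAP Emax | 24% |
| SAP exponential | 12% |
| SAP sigmoid Emax | 34% |
| Linear | 26% |
| Emax, ED50 1 | 38% |
| Hill, ED50 1, slope 2 | 40% |
| No effect | 6% |

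The best of a grid of monotone truths reached 46% (42% at SD 5.3; 49% with 57 per arm).

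**Sensitivity.** At SD 4.0 the SAP's shapes give 12% to 40%, and the most favourable truth 58%. At SD 5.0 with a favourable Hill shape (ED50 0.7, slope 3), top-dose effects of 4 and 6 points give 62% and 85%.

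**Uncorrected curve.** It must pass through the three active means while held at 0 for placebo. At SD 5.0 and effect 3, finite estimates exist in 3% to 46% of trials with no placebo change, and in 9% to 69% with a placebo change of −1 to −3.

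**Precision when a finite fit exists** (placebo-corrected, SD 5.0, non-flat truths). The median SE of n is 1.5 to 2.5. Even at 1.5, the 95% limits multiply or divide the slope by exp(1.96 × 1.5), about 19. The Wald interval for a excludes 0 in 28% to 68% of these fits, which is 3% to 31% of all trials.

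**The case against.** Four points on the other side are sound.

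- **The promise of SEs and CIs belongs to the uncorrected curve.** A reader might attach it to the placebo-corrected variation; the text does not. The uncorrected curve meets the same obstacle, so a rule is needed for both.
- **Saturation alone does not remove standard errors.** With 200 subjects and four parameters, about 196 within-arm degrees of freedom remain. A reader might infer that equal counts make estimation impossible. The failure comes from saturation together with the shape restriction.
- **Failure in most trials is not a general result.** It holds for every monotone shape scanned for the placebo-corrected curve at SD 5.0 to 5.3 with a 3-point effect. It does not hold at SD 4.0 with a favourable shape, nor with clearly larger effects.
- **The stakes are limited.** A reader might infer that dose selection or the main result is compromised. Nothing in the documents uses this ED50 or ED90 to select a dose. Dose response is also covered by MCP-Mod (10.1.3) and by the linear, quadratic and cubic contrasts in 10.1.

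It can also be said that fixing the slope largely repeats the MCP-Mod Emax model and is misspecified for two of the three candidate shapes. That stands. With e^n = 1 the fit has an interior optimum in about 75% of trials under the SAP Emax, 64% under the sigmoid, 50% under a linear shape and 20% under the exponential. Its profile interval for ED50 would extend past 3 mg/d in about 56% of trials under the SAP Emax and 99% to 100% under the other two candidates. A reduced model is therefore only a fallback. The estimability rule and honest limits are the substance of the change.

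**Conclusion.** The point holds as a gap in a sensitivity analysis. At the planning values, the placebo-corrected curve yields finite estimates in about 12% to 34% of trials under the SAP's own shapes and at most about 46% under any monotone shape scanned. In the rest, the estimates lie at a boundary and Wald SEs and intervals for a, b and n have no useful meaning. The uncorrected curve is also affected, to a degree that depends on the placebo change.

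These figures assume 50 analysed per arm, normal arm means, a 3-point effect at the top dose, SD 5.0 and no baseline term (the formula has none). The parameter count and the existence condition do not depend on those values. The primary ANCOVA and its conclusion are untouched.

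**What to change.** Amend SAP 10.1.5, for both versions of the curve, before unblinding:

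1. State whether P is estimated jointly. Fix k below 1, because at the permitted k = 1 both b and n drop out of the formula.
2. Give parameter bounds, starting values and a convergence rule. Treat a solution at a bound as not estimable.
3. Replace Wald limits for ED50/ED90 with profile-likelihood or bootstrap limits, and report not estimable when the interval is unbounded.
4. Name a reduced model as the fallback, for example P estimated with the shape fixed at e^n = 1. Say that it assumes the slope, overlaps the MCP-Mod Emax model and does not guarantee an estimable ED50.

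The cost is SAP wording and minor programming. In many trials the report will say that the ED50 could not be determined, and where the fallback is used the slope is assumed, not estimated.
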